9 HUMAN SUBJECTS PROTECTION

9.1 Institutional Review Board/Independent Ethics Committee

The site principal investigator will obtain IRB approval for this protocol to be conducted at his research site and send supporting documentation to the DMID before initiating recruitment of subjects. The investigator will submit applicable information to the IRB/IEC on which it relies for the review, to conduct the review in accordance with 45 CFR 46, ICH E6 GCP, and as applicable, 21 CFR 56 (Institutional Review Boards) and 21 CFR 50 (Protection of Human Subjects), other federal, state, and local regulations. DMID must receive the documentation that verifies IRB/IEC-approval for this protocol, associated informed consent documents, and upon request any recruitment material and handouts or surveys intended for the subjects, prior to the recruitment and enrollment of subjects.

Any amendments to the protocol or consent materials will be approved by the IRB/IEC before they are implemented. IRB/IEC review and approval will occur at least annually throughout the enrollment and follow-up of subjects and may cease if annual review is no longer required by applicable regulations. The investigator will notify the IRB/IEC of deviations from the protocol and reportable SAEs, as applicable to the IRB/IEC policy.

9.2 Informed Consent Process

Informed consent is a process that is initiated before an individual agrees to participate in a trial and continuing throughout a subject's participation in a trial. Before any trial procedures are performed, informed consent will be obtained and documented. Subjects will receive a concise and focused presentation of key information about the clinical trial, verbally and with a written ICF. The explanation will be organized and presented in lay terminology and language that facilitates understanding why one might or might not want to participate.

The Site PI or designee will describe the protocol to potential subjects face-to-face. The key information about the purpose of this trial, the procedures and experimental aspects of this trial, risks and discomforts, and any expected benefits to the subject will be presented first to the subject.

Subjects will also receive an explanation that this trial involves research, and a detailed summary of the proposed trial procedures and trial interventions/drugs. This will include aspects of this

trial that are experimental, the probability for random assignment to study drug groups, any expected benefits, all possible risks (including a statement that particular study drugs or procedures may involve risks to the subject or to the embryo or fetus, if the subject is or may become pregnant, that are currently unforeseeable), and the expected duration of the subject's participation in this trial.

Subjects will be informed that they will be notified in a timely manner if information becomes available that may be relevant to their willingness to continue participation in this trial. Subjects will receive an explanation as to whether any compensation and any medical treatments are available if injury occurs, and, if so, what they consist of, or where further information may be obtained. Subjects will be informed that there are no financial expenses to the subject for participating in this trial, as well as be informed of the anticipated prorated payments to the subject for participating in this trial. They will be informed of whom to contact (e.g., the Site PI) for answers to any questions relating to this trial.

Information will also include the foreseeable circumstances and/or reasons under which the subject's participation in this trial may be terminated. The subjects will be informed that participation is voluntary and that they are free to withdraw from this trial for any reason at any time without penalty or loss of benefits to which they were otherwise entitled.

The extent of the confidentiality of the subjects' records will be defined, and subjects will be informed that applicable data protection legislation will be followed. Subjects will be informed that the monitor(s), auditors(s), IRB, NIAID, and regulatory authorities will be granted direct access to the subject's original medical records for verification of clinical trial procedures and/or data without violating the confidentiality of the subject, to the extent permitted by the applicable laws and regulations, and that, by signing a written ICF, the subject is authorizing such access.

Subjects will be informed that records identifying the subject will be kept confidential and, to the extent permitted by the applicable laws and/or regulations, will not be made publicly available and, if the results of this trial are published, the subject's identity will remain confidential. Subjects will be informed whether confidential information collected from this research and/or specimens will be used for additional research, even if identifiers are removed.

Subjects will be allowed sufficient time to consider participation in this trial and to discuss this trial with their family, friends, or legally authorized representative, or think about it before agreeing to participate.

ICFs will be IRB-approved and subjects will be asked to read and review the ICF. Subjects will sign the ICF before starting any trial procedures being done specifically for this trial.

Once signed, a copy of the ICF will be given to the subject(s) for their records. The subject(s) may withdraw consent at any time throughout the course of this trial. The rights and welfare of the subject(s) will be protected by emphasizing to them that the quality of their medical care will not be adversely affected if they decline to participate in this trial.

Trial personnel may employ recruitment efforts before obtaining trial consent if a patient-specific screening consent is on record or if the IRB has agreed that chart review is allowed without a fully executed screening consent. In cases where there is not a patient-specific screening consent on record, site clinical staff may pre-screen via chart review and refer potential subjects to the research staff. Research staff would obtain written consent per the standard informed consent process before conducting protocol-specific screening activities.

New information will be communicated by the Site PI or delegated staff to subjects who consent to participate in this trial in accordance with IRB requirements. The ICF will be updated and subjects will be re-consented per IRB requirements, if necessary. Subjects will be given a copy of all ICFs that they sign.

9.3 Consent for Future Use of Stored Specimens and Data

Residual clinical samples will be available upon the completion of the study; however, future use clinical samples may be requested from DMID and shipped from the DMID CMS at any time. These clinical samples will be shipped to and stored for up to 2 years at the Fisher Biorepository (DMID CMS).

The samples will not be sold or used directly for production of any commercial product. No human genetic tests will be performed on the samples. Each sample will be encoded (labeled) only with a barcode and a unique tracking number to protect subject confidentiality. The recipients of specimens will be informed that these specimens have a NIH certificate of confidentiality.

There are no benefits to subjects in the collection, storage and subsequent use of their specimens for future research. Reports about future research done with subjects' samples will NOT be kept in their health records.

Subjects may be given the option to decide if they want their residual specimens to be used for future research or have these specimens destroyed at the end of this trial. The subject's decision can be changed at any time by notifying the study doctors or nurses in writing. However, if the subject originally consents to the future use of residual specimens and subsequently changes his/her decision, any data from a previously collected specimen may still be used for future research.

9.4 Exclusion of Women, Minorities, and Children (Special Populations)

Children aged <18 years and elderly populations will be excluded from participation because insufficient data are available in adults to judge potential risk in children and elderly individuals, and as a Phase 1 trial in healthy subjects, there is no known benefit. For these same reasons, this trial will not include other special classes of subjects, such as fetuses, neonates, prisoners, institutionalized individuals, or others who may be considered vulnerable populations.

Neither women nor minorities will be excluded from participation in this trial. Women of child-bearing potential may be included as per the inclusion criteria ([Section 5.1.1](#)). Subjects will be recruited without regard to gender or race. It is expected that race will reflect that within the community.

9.5 Subject Confidentiality

Subject confidentiality is strictly held in trust by the participating PI's, their staff, and the Sponsor and their agents. This confidentiality includes documentation, investigation data, subject's clinical information, and all other information generated during participation in this trial. No information concerning this trial, or the data generated from this trial will be released to any unauthorized third party without prior written approval of the DMID and the subject. Subject confidentiality will be maintained when trial results are published or discussed in conferences. The trial monitor or other authorized representatives of the Sponsor or governmental regulatory agencies may inspect all documents and records required to be maintained by the PI, including but not limited to, medical records (office, clinic, or hospital) and pharmacy records for the subjects in this trial. The CRU will permit access to such records.

All records will be kept locked and all computer entry and networking programs will be carried out with coded numbers only and with password protected systems. All non-clinical specimens,

evaluation forms, reports, and other records that leave the site will be identified only by a coded number.

9.6 Certificate of Confidentiality

To protect privacy, we have received a Certificate of Confidentiality. With this Certificate, the researchers cannot be forced to release information that may identify the research subject, even by a court subpoena, in any federal, state, or local civil, criminal, administrative, legislative, or other proceedings. The researchers will use the Certificate to resist any demands for information that would identify the subject, except as explained below.

The Certificate cannot be used to resist a demand for information from personnel of the US Government that is used for auditing or evaluation of federally funded projects, like this trial, or for information that must be released in order to meet the requirements of the FDA.

A Certificate of Confidentiality does not prevent the subject from voluntarily releasing information about themselves or their involvement in this research. If any person or agency obtains a written consent to receive research information, then the researchers may not use the Certificate to withhold that information.

The Certificate of Confidentiality does not prevent the researchers from reporting without the subject's consent, information that would identify the subject as a participant in the research project regarding matters that must be legally reported including: child and elder abuse, sexual abuse, or wanting to harm themselves or others.

The release of individual private information or specimens for other research will only occur if consent was obtained from the individual to whom the information, document, or biospecimen pertains, *or* for the purposes of other research that is in compliance with applicable Federal regulations governing the protection of human subjects in research.

9.7 Costs, Subject Compensation, and Research Related Injuries

There is no cost to subjects for the research tests, procedures, and study drug while participating in this trial. Procedures and treatment for clinical care may be billed to the subject, subject's insurance, or third party.

Subjects may be compensated for their participation in this trial. Compensation will be in accordance with the local IRB's policies and procedures, and subject to IRB approval.

If the Site PI determines that an injury occurred to a subject as a direct result of the tests or treatments that are done for this trial, then referrals to appropriate health care facilities will be provided to the subject. Trial personnel will try to reduce, control, and treat any complications from this trial. Immediate medical treatment may be provided by the site. No financial compensation will be provided to the subject by the NIAID, NIH to the subject, or by the participating site for any injury suffered due to participation in this trial.

10 STATISTICAL CONSIDERATIONS

A formal Statistical Analysis Plan (SAP) will be created prior to database lock. This document will provide a more technical and detailed description of the proposed data analysis methods and procedures. Any deviation from the analysis outlined in the protocol will be described in the SAP.

For continuous variables, data will be summarized using descriptive statistics (such as sample size, mean, median, standard deviation, minimum, and maximum). For discrete variables, data will be summarized using frequencies and percentages.

10.1 Study Hypotheses

The objectives of this trial are to obtain safety, tolerability, and PK data for rezafungin. There are no formal hypotheses being tested in this trial.

10.2 Sample Size Considerations

No formal sample-size calculations based on testing a statistical hypothesis were constructed. There will be a total of 86 subjects in this three-part trial, 44 subjects in 6 cohorts will receive rezafungin or placebo via SC injection in Part 1/SAD, 32 subjects in 4 cohorts will receive rezafungin or placebo via SC injection in Part 2/MAD, and 10 subjects will receive rezafungin via both SC and IV injections in Part 3/BA. The number of subjects was selected to allow sufficient evaluation of safety, tolerability, and PK of the various dose regimens, and to be consistent with standards of practice for Phase 1 trials.

10.3 Treatment Assignment Procedures

10.3.1 Randomization Procedures

Each subject who completes the Screening assessment, meets all eligibility criteria, and is enrolled into this trial will randomized to rezafungin or placebo (Cohorts 1-10) or randomized to treatment sequence (Cohort 11),, except for replacement subjects. Replacement subjects will be assigned the same study drug dosing regimen as the replaced subject.

The randomization schedule will be generated centrally through AdvantageEDCSM (Electronic Data Capture [EDC] System, Emmes) by the unblinded biostatistician, and a list will be transferred to the unblinded Site Pharmacist before the start of this trial as an emergency back-up. Part 1 Cohort 1 will have 4 subjects randomized 3:1 to receive rezafungin or placebo, respectively. There will be no sentinel dosing for Cohort 1. Within cohorts 2-6 in Part 1 and all cohorts of Part 2, 8 subjects will be randomized 3:1 to receive rezafungin or placebo, respectively. In each dosing cohorts 2-6 in Part 1 and all cohorts of Part 2, the first two subjects will be randomized 1:1 to receive rezafungin or placebo to ensure that one of the first two subjects receives rezafungin and the other placebo. The study drug assignment of the remaining subjects in each cohort will be randomly assigned in a 5:1 ratio of active drug to placebo to ensure the 3:1 ratio for the entire dosing cohort. In Part 3, 10 subjects will be randomized in a 1:1 ratio of dose route order (SC → IV or IV → SC). Enrollment will occur at one CRU.

Per ICH guideline E6: GCP, screening records that document why an individual was screened but not enrolled will be kept at the CRU. Reasons for screen failures will also be recorded in AdvantageEDCSM.

Subjects will be enrolled online using the enrollment module of AdvantageEDCSM. The randomization code will be prepared by statisticians at the SDCC and included in the enrollment module for this trial. AdvantageEDCSM will assign each subject to a rezafungin or placebo group after demographic and eligibility data have been entered into the system. A designated individual at the CRU will be provided with a code list for emergency unblinding purposes, which will be kept in a secure place.

Instructions for using the enrollment module are included in the AdvantageEDCSM User's Guide. Manual back-up procedures and instructions are provided for use in case the CRU temporarily loses access to the Internet or the online enrollment system is unavailable.

10.3.2 Masking Procedures

10.3.2.1 Blinding

For SAD and MAD subjects, the Site Pharmacist will be unblinded as to randomization assignment. Subjects, the PI, and CRU personnel other than the Site Pharmacist, the bioanalytical laboratory staff, and Fisher repository personnel will remain blinded to all randomization assignments. The PK analyst(s) will be unblinded. The DMID Medical Monitor, other NIAID personnel, and ICON personnel will remain blinded to all randomization

assignments. For subjects enrolled in Part 3 (Bioavailability), the subjects, the PI, and CRU personnel will be unblinded to randomization assignment.

Selected individuals not involved in conducting this trial, including members of the SMC, may have access to the unblinded data as needed for safety or other data review. The Site Pharmacist will remain unblinded during this trial.

10.3.3 Emergency Unblinding

Emergency unblinding of study drug assignment for a subject may be necessary due to a medical emergency, or any other significant medical event, if knowledge of the subject's study drug assignment impacts the subject's care. If an SAE or other circumstance requires the blind to be broken to ensure a subject's safety, the PI will immediately notify the DMID Medical Monitor if possible (within 24 hours) to discuss the case and reason for unblinding (a written narrative will follow within 48 hours of the event).

Procedures for emergency unblinding are detailed in the MOP for this trial.

10.4 Planned Interim Analyses

10.4.1 Interim Safety Review

An interim safety review will be performed upon completion of the SAD cohorts (1-6) and prior to starting the MAD and BA parts of the study.

An interim safety review will also be performed by the SMC upon completion of Day 30 for all subjects upon completion of the SAD cohorts (1-6) and prior to starting the MAD and BA parts of the study. This safety review may include but is not limited to enrollment, laboratory, and safety data. If criteria for halting the trial (as listed in [Section 8.7](#)) are met, an *ad hoc* SMC meeting will be held to review all available safety data and to make recommendations about the dosing of all further subjects in the trial. The SMC will receive data presented in aggregate (by cohort). Analysis by treatment assignment may be provided to the SMC in the closed session only.

10.4.2 Interim Immunogenicity or Efficacy Review

An interim PK analysis will be conducted upon the completion of the SAD cohorts (2-6).

All safety and PK data will be provided to the FDA for review prior to initiation of the MAD and BA portions of the trial. FDA will approve continued enrollment in the MAD and BA parts of the study and possibly recommend dose changes.

10.5 Final Analysis Plan

The safety analysis population will include all subjects that received any amount of study product and will be analyzed by treatment received. All subjects who receive a dose of rezafungin or placebo will be included in the safety analysis population. All subjects who receive a dose of rezafungin and have at least 1 measurable drug concentration after dosing in plasma will be included in the PK analysis population.

Placebo subjects may be pooled across multiple cohorts for analysis. The PK analysis population will include all subjects with at least one measurable rezafungin plasma concentration. Missing data will not be imputed. Details of study analyses for safety and PK data and their presentation will be fully described in the SAP, prepared by the SDCC and finalized prior to data lock.

10.5.1 Adverse and Serious Adverse Events

AEs will be coded using Medical Dictionary for Regulatory Activities® (MedDRA). All AEs occurring after study drug dosing will be summarized using frequency counts and percentages. Summaries will be presented by dose cohort and control group. The following summaries will be presented for AEs and SAEs:

- Overall (i.e., regardless of severity or relationship to study drug),
- By severity grade (mild, moderate, or severe),
- By relationship to study drug,
- By MedDRA level hierarchy (system organ class, HLGT and preferred term).

Unless otherwise specified, at each level of subject summarization in reporting the incidence of the AEs, a subject will be counted once if the subject reported one or more AEs. If more than one occurrence of an AE is reported, the AE of the worst severity or the worst-case relationship assessment will be summarized. For crossover data, AEs will be summarized separately for each

treatment and the worst severity and worst-case relationship after each treatment will be summarized. An AE that began after the first treatment, continued into the second period, and worsened in severity after the second treatment will be considered a new AE associated with the second treatment.

10.5.2 Clinical Safety Labs, Vital Signs, and Electrocardiograms

Baseline for clinical safety labs, vital signs, and ECGs will be defined as the last result obtained before the dose of study product. For crossover data, there will be a separate baseline for each treatment. Changes from baseline for clinical safety labs, vital signs, and ECGs results will be summarized by dose group and time point. Clinical safety labs and vital signs will be graded ([Appendix B](#)) and summarized by severity, group, and visit. Rules for analyzing replicates for a safety time point (labs, vital signs, ECG), if obtained, will be described in the SAP.

Treatment-emergent abnormal laboratory test results will be identified. Treatment-emergent abnormal laboratory tests are tests for which the result was not graded as mild or worse at baseline but graded as mild or worse after dosing. Laboratory tests graded as mild at baseline, but moderate or worse any time after dosing will also be regarded as treatment-emergent abnormal laboratory test results.

ECG measurements will include heart rate, RR interval, QT interval, QTcF interval, PR interval, and QRS duration. Baseline for ECG measurements is defined per protocol as the value pre-dosing on Day 1 (or pre-dosing on Day 21 for period 2 of Part 3). Change from baseline will be summarized descriptively by regimen at each scheduled evaluation. QTc results will be summarized categorically according to the ICH Guideline E14 “Clinical Evaluation of QT/QTc Interval Prolongation and Proarrhythmic Potential for Non-Antiarrhythmic Drugs” (October 2005):

- QTcF >450 ms, males only
- QTcF >470 ms, females only
- QTcF >480 ms
- QTcF >500 ms
- QTcF increases from baseline by at least 30 ms but less than 60 ms
- QTcF increases from baseline by at least 60 ms

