3.1.1.3 Part 3 (BA)

Part 3 of this study may be run in parallel with Cohort 7 of the Part 2 (MAD) portion of this study, upon completion of safety data review for all Cohorts 1-6 of Part 1 (SAD). In the unblinded Part 3 cross-over portion of this trial, 10 subjects will be randomized to one of two sequences of 5 subjects each to receive a SC→IV or IV→SC sequence of study drug administration. In sequence 1 (SC→IV), rezafungin (100 mg or MTD in Part 1) administered by SC injection on Day 1 followed by rezafungin (100 mg or MTD in Part 1) administered by IV infusion over 60 minutes on Day 22; or in Sequence 2 (IV→SC), rezafungin (100 mg or the maximum tolerated dose in Part 1) administered by IV infusion over 60 minutes on Day 1 followed by rezafungin (100 mg or the maximum tolerated dose in Part 1) administered by SC injection on Day 22. Maximum tolerated dose (MTD) is defined as the highest dose level with no withdrawals by subject or investigator due to AEs related to study product for Part 1 (SAD) Cohorts 1-6. A schematic of the BA study design is shown in [Table 3](#).

Table 3: Design for SC Dosing in Absolute BA Cohort (Study Part 3)

Sequence		Day 1 (Period 1) Dose/Volume/Route	Day 22 (Period 2) Dose/Volume/Route	Number of Subjects*
1 (SC → IV)		100 mg x 1 mL SC injection	100 mg 250 mL IV infusion	5
2 (IV → SC)		100 mg 250 mL IV infusion	100 mg 1 mL SC injection	5
Total Number of Subjects				10

*Part 3 may be run following the cohort dosed at the same dose level (100 mg or MTD) in Part 1 (SAD).

The BA of the SC dose compared to the IV dose will be determined as the ratio of the rezafungin area under the plasma concentration versus time curve (AUC) values from each administration.

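### Protocol 10.5.2 takes the Part 3 Period 2 ECG baseline from Day 21, when no dose is given and no ECG is scheduled, and other sections do not clearly schedule a pre-dose ECG on the actual dosing day, Day 22 (low priority)

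*Protocol*

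**What the plan says.** Protocol 10.5.2 contains three statements that bear on the Period 2 baseline in the crossover.

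- A general rule covers laboratory tests, vital signs and ECGs: baseline "will be defined as the last result obtained before the dose of study product".
- A crossover rule follows: "For crossover data, there will be a separate baseline for each treatment".
- An ECG-specific rule then fixes the baseline at the Day 1 pre-dose value, "or pre-dosing on Day 21 for period 2 of Part 3".

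The same section lists what is measured ("ECG measurements will include heart rate, RR interval, QT interval, QTcF interval, PR interval, and QRS duration") and how it is reported: "Change from baseline will be summarized descriptively by regimen at each scheduled evaluation". Two of its six QTcF categories are defined by increase from baseline. Section 10.5 adds: "Missing data will not be imputed".

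On the design, Section 3.1.1.3 says "10 subjects will be randomized to one of two sequences of 5 subjects each". The second dose in both sequences is on Day 22; for the IV-first sequence it is "administered by SC injection on Day 22". Section 6.6.1 and Table 13 footnote g give the same dosing days, 1 and 22. Section 6.3 makes Day 21 the admission day before that dose.

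**The concern.** The analysis section names a baseline that the visit schedule does not supply. Day 21 is not a dosing day, and reading the phrase as the admission day does not help, because no ECG is listed for admission.

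At stake is the ECG safety comparison of the two routes in Part 3: change from baseline after the second dose, and the two QTcF-increase categories. The four categories based on absolute QTcF, and the bioavailability endpoint, do not use this baseline.

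**Working it through.** No figure in the plan needs reproducing here. The check is a comparison of passages followed by a count.

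**1. Dosing day.** Period 1 is dosed on Day 1 and Period 2 on Day 22. The interval is 22 − 1 = 21 days, or 21 × 24 = 504 h. A value taken before the Period 2 dose on the dosing day itself therefore falls on Day 22.

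**2. Is there an ECG on Day 21?** No. The admission list in Section 6.3 has none. The ECG row of Table 13 is blank in the column for Days -1 and 21. Section 7.1.6 adds only Day 52 and unscheduled visits for the bioavailability part.

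**3. Is there a pre-dose ECG on Day 22?** The documents do not settle this.

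| Place | What it supports |
|---|---|
| Section 6.6.1 (headed Days 1 and 22) | Pre-dose ECG limited to Day 1; the only explicit restriction |
| Table 13 footnote j | Names the Day 1 pre-dose ECG only. It names no Day 22 ECG of either kind, so its silence is weak evidence |
| Table 13, ECG row | Marked under Days 1/22, but a Day 22 post-dose ECG alone would satisfy the mark |
| Section 7.1.6 | Gives a 60-minute window for pre-dose ECGs on dosing days, across all parts, and refers to Appendix A for the times |
| Section 10.5.2 | Presupposes a Period 2 pre-dose ECG |

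Section 7.1.6 cannot decide the matter alone. Part 2 has three dosing days, yet Section 6.5.1 also limits its pre-dose ECG to Day 1.

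**4. What each baseline rule yields if only Day 1 has a pre-dose ECG.**

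- The ECG-specific rule yields no Period 2 value.
- The general rule yields the last ECG before the Day 22 dose, which is the Day 1 post-dose ECG. After SC dosing it is taken at 4 h, so 504 − 4 = 500 h before the Period 2 dose. After IV dosing it is taken 1 h from the start of infusion, so 504 − 1 = 503 h before. In both cases the Period 1 dose has already been given or is being completed.

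**5. How many values depend on it.** The inputs are 10 subjects; post-dose ECGs on Days 1 and 22 (the post-dose items in Section 6.6.1 carry no day limit) and on Day 52 (Section 6.6.9); and six measurements (Section 10.5.2).

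- Post-dose evaluations: 10 × 3 = 30. After the second dose: 10 × 2 = 20.
- Change values: 30 × 6 = 180. After the second dose: 20 × 6 = 120.
- QTcF categories that need a baseline: 2 of 6.
- If footnote j is read strictly, with no Day 22 ECG at all, the counts fall to 10 of 10 × 2 = 20 evaluations and 60 of 120 change values.
- If a Day 22 pre-dose ECG is taken and used as baseline, the count is 0.

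**6. Effect on the summary by regimen.** Each route is given to 5 subjects in Period 1 and 5 in Period 2. With no Period 2 baseline, dosing-day change for each route would rest on 5 of 10 subjects. Under the general rule all 10 would contribute, but 5 would be compared with an ECG recorded after the other route's dose.

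**The case against.** The best reply is that this is a one-digit slip and that 10.5.2 still works. Its general rule always returns some earlier ECG, so a change from baseline can be computed for every subject. A reader might infer from the ECG-specific sentence that the Period 2 changes could not be calculated and that all 120 values would be lost. The documents do not support that as a flat statement. It holds only if the ECG-specific sentence overrides the general one and no Day 22 pre-dose ECG is taken, and the same condition applies to the figure of 5 of 10 subjects per route.

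Part of the reply fails. Replacing 21 with 22 leaves 10.5.2 in conflict with Section 6.6.1. The value that the general rule returns is not a pre-dose baseline in any useful sense: it follows the Period 1 dose, and any ECG effect present at that time would be built into the reference for Period 2.

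A second fair reply is that the procedural text may be consistent, with a pre-dose ECG on Day 1 only and Section 7.1.6 giving just a time window. That reading is open. It makes the phrase in 10.5.2 the sole outlier but does not give it an ECG to point to. Equally, a reader might infer that a Day 22 pre-dose ECG was intended and omitted by mistake. The documents do not establish that either.

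**Conclusion.** The ECG-specific baseline rule for Part 3 Period 2 fails as written, and correcting the day number alone does not repair it. Its reach runs from 0 to 20 of 30 post-dose evaluations (0 to 120 of 180 change values), plus the two QTcF-increase categories, depending on whether a Day 22 pre-dose ECG is taken. At the upper end the values have either no baseline or one recorded after the Period 1 dose, depending on which sentence of 10.5.2 governs. The upper end assumes all 10 planned subjects complete the scheduled ECGs, including a post-dose ECG on Day 22.

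Priority is low. The SAP preface records that nobody was enrolled in the bioavailability cohort, and the SAP analyses only the first two single-dose cohorts. Its ECG baseline (Section 3.3.2) has no Period 2 rule, so it does not cure the protocol text, but no reported result depends on it. The point matters for the protocol as written and for any re-use of the Part 3 design. It takes no position on which ECG schedule is right.

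**What to change.** Reconcile Protocol 10.5.2, 6.6.1, 7.1.6 and Table 13 footnote j so that the ECG named as the Period 2 baseline is one that is scheduled before the Period 2 dose. Footnote j should also say which ECGs are taken on Day 22. Any edit to 7.1.6 should be made by part, so that the Part 2 text in Section 6.5.1 is not altered by accident.

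If no ECG is intended between Day 1 and the second dose:

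- remove the Day 21 phrase and state which scheduled pre-dose ECG serves as the Period 2 baseline;
- exempt Part 3 ECGs from the last-result and separate-baseline sentences;
- state the limitation, namely that Period 2 changes then include between-period drift and any residual effect of the first dose.

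The cost is wording in up to four places. If the sponsor's intention is a Day 22 pre-dose ECG, that is one triplicate set per subject beyond what Section 6.6.1 now lists: 10 sets, or 10 × 3 = 30 tracings. Because 7.1.6 ties the Day 1 pre-dose ECG to the decision to dose, the sponsor would then also need to make clear whether the Day 22 ECG has any such role. The alternative adds no procedure.
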